11.4.5 Deviation(s) from the original statistical plan

No deviation is planned.

11.5 Handling of missing data and drop-outs

There will be no imputation for missing values. Missing values are reported and only available data are used for descriptive analysis.

Drop-outs will not be replaced.

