MedDO	Medical Devices Ordinance (in German: MepV, in French: Odim, in Italian: Odmed)
MD	Medical Device
MDR	Medical Device Regulation (EU) 2017/745 of 5 April 2017
PI	Principal Investigator
SADE	Serious Adverse Device Effect
SAE	Serious Adverse Event
SDV	Source Data Verification
SNCTP	Swiss National Clinical Trials Portal
SOP	Standard Operating Procedure
USADE	Unanticipated Serious Adverse Device Effect

SUMMARY OF THE REVISION HISTORY IN CASE OF AMENDMENTS

Not applicable

INVESTIGATION SCHEDULE

Study Periods	Screening	Intervention Period	In-hospital follow-up	Follow-up
Visit	1	2	3	4
Time (day)	-5/14	0	2	30
Patient Information and Informed Consent	x			
Demographics	x			
Medical History	x			
In- /Exclusion Criteria		x		
Physical Examination			x	x
Vital Signs		x	x	
Laboratory Tests			x	
Pregnancy Test		x		
Operation with use of Medical Device		x		
Primary Variables		x	x	x
Secondary Variables		x	x	
Adverse Events		x	x	x

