5. CLINICAL INVESTIGATION OUTCOMES

5.1 Primary Outcome

The primary outcome will evaluate the safety of the use of the Senhance™ Surgical System in bariatric surgery.

Intraoperative complications such as bleeding, organ lesion, and procedure interruption will be monitored during the operation and reported postoperatively.

Postoperative complications and re-operation will be reported at discharge and at the 30-days follow up control. Complications will be classified according to its gravity by the Clavien-Dindo classification and by its type (postoperative bleeding, anastomotic or staple line leakage, surgical site infection, cardiovascular complication, respiratory complications, thromboembolic complication, renal complication...).

30-day postoperative mortality (= Clavien Dindo grade V) will be reported at discharge and at the planned 30-day-checkup.

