11.2 Determination of Sample Size

The study is designed as single arm, two-stage phase II study with a stopping rule for safety using the Simon's two-stage design.

Literature shows a complication rate for conventional laparoscopic bariatric surgery of 10%. We expect to have similar complication rates with bariatric surgery. For calculation of the safety stopping point we set the maximum acceptable threshold of complications at 25%.

We used Simon's 2 stage design to derive the time point of an interim analysis and a stopping rule for safety, assuming Type I error to be 0.05 and Type II error 0.8.

Simon's optimal two-stage design yielded the following numbers with respect to a 25% threshold:

- Interim analysis will be done at 22 patients. If there are 5 or more events, the study will stop for safety.
- Final analysis will be done at 39 patients. Robotic surgery can be regarded as successful if less than 6 events occurred.

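### Fixed event limits with available-data handling: a complication after discharge that only a missed day-30 visit would have revealed counts as no event, and alpha has no slack to absorb it

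*Protocol*

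**What the plan says.** Protocol section 11.2 sets the decision rule as absolute counts. For the interim: "Interim analysis will be done at 22 patients. If there are 5 or more events, the study will stop for safety". For the end of the trial: "Robotic surgery can be regarded as successful if less than 6 events occurred". Section 11.4.4 repeats the interim limit and ties that analysis to the inclusion of 22 participants.

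Section 5.1 gives the reporting points for the postoperative part of the primary outcome: "Postoperative complications and re-operation will be reported at discharge and at the 30-days follow up control". The investigation schedule agrees. Its row "Primary Variables" is marked at day 0, day 2 and day 30, with no contact between the last two. Section 10.4 likewise has adverse events collected systematically during the hospital stay and at the 30-day visit.

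Section 11.5 is the only text on missing data. It excludes imputation, says that "Missing values are reported and only available data are used for descriptive analysis", and says that drop-outs are not replaced. No section says how an operated patient without a day-30 assessment enters the stop or success rule, and none requires the site to contact such a patient. Sections 8.4 and 9.2.5 deal with withdrawal and premature stopping, which is a different situation.

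**The concern.** A limit expressed as a count does not adjust when information is lost. Whether a patient with no day-30 data stays in as event-free or is dropped from a percentage, the comparison is still with 5 and 6 events. A missed visit can therefore lower the count or leave it unchanged, but never raise it.

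Leakage, surgical site infection and thromboembolism, all named in the Protocol as common complications, can appear after a short hospital stay (2–3 days in section 10.4, 3–4 days in section 9.3.2). A patient treated for one of these elsewhere might also be one who does not attend.

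The trial's main product is a safety verdict that turns on one event (5 against 6), so a one-directional loss toward safe deserves a safeguard.

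**Working it through.** **Inputs from section 11.2.** Unacceptable rate: "we set the maximum acceptable threshold of complications at 25" per cent. Expected rate: "Literature shows a complication rate for conventional laparoscopic bariatric surgery of 10" per cent. Error rates: "assuming Type I error to be 0.05 and Type II error 0.8"; the second figure only makes sense as power, and is read so here. Limits: continue with at most 4 events in 22, success with at most 5 in 39 (22 + 17).

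**Inputs assumed.** Each patient counts for at most one event. A patient who misses day 30 has observable event probability p(1 − q), where q is the share of risk that only the visit would reveal. The Protocol gives neither q nor the number of missed visits, so both are varied.

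**Step 1: reproduce the plan.**
P(success) = Σ over x = 0…4 of Bin(x; 22, p) × P(Y ≤ 5 − x), with Y ~ Bin(17, p).

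At p = 0.25 the five terms are 0.0014 + 0.0075 + 0.0162 + 0.0167 + 0.0081 = 0.0498 after rounding once at the end. At p = 0.10 the sum is 0.8024. The stated limits thus meet alpha 0.05 and power 0.80, with 0.0002 of alpha to spare.

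**Step 2: missed day-30 visits in stage 2, limits unchanged.** Replace Y by the sum of Bin(17 − m, 0.25) and Bin(m, 0.25(1 − q)). Chance of success at a true 25% rate:

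| Missed visits m | q = 0.25 | q = 0.50 | q = 0.75 |
|---|---|---|---|
| 0 | 0.050 | 0.050 | 0.050 |
| 1 | 0.052 | 0.054 | 0.056 |
| 2 | 0.054 | 0.059 | 0.064 |
| 4 | 0.059 | 0.069 | 0.081 |

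**Step 3: missed visits in both stages.** With two in each stage and q = 0.50, alpha is 0.070. The chance of the interim stop at a true 25% rate falls from 0.677 to 0.632.

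**Step 4: the cost of the opposite rule.** Suppose each patient of unknown status is counted as an event. With k1 unknown in stage 1 and k2 in stage 2 (k = k1 + k2), success at p = 0.10 is Σ over x = 0…4 − k1 of Bin(x; 22 − k1, 0.10) × P(Y ≤ 5 − k − x), with Y ~ Bin(17 − k2, 0.10).

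| Unknown patients | P(success) at 10% | P(interim stop) at 10% |
|---|---|---|
| None | 0.802 | 0.062 |
| One, stage 1 | 0.653 | 0.152 |
| One, stage 2 | 0.670 | 0.062 |
| Two, stage 1 | 0.455 | 0.323 |
| Two, stage 2 | 0.486 | 0.062 |

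For one patient in stage 2 with q = 0.50, the present rule adds about 0.004 to alpha (0.054 − 0.050). Counting that patient as an event takes about 0.13 from power (0.802 − 0.670).

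**The case against.** The strongest reply is that the visit is not the only route by which an event becomes known. Section 9.2.4.1 has any adverse event up to 30 days reported, section 10.4.2 has serious events sent to the sponsor-investigator within 24 hours of awareness, and section 12.2.1 draws study data from the hospital information system as well as the paper forms. A readmission to the same hospital would probably be counted. This stands, and it limits the point to events treated elsewhere or never reported.

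A reader might infer that a patient who misses day 30 contributes no event information at all. The documents do not support that. Such a patient was observed through surgery and seen daily until discharge, so q = 1 is not a realistic bound and is left out of the table.

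Non-attendance may also be rare: section 10.4 describes the 30-day visit as usual for all bariatric patients at the centre. With one or two missed visits the inflation is small. That stands too.

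Two other replies carry less weight. Section 11.5 speaks of descriptive analysis, so applying it to the decision is an inference. But the decision is a count of those same described events, and no other text governs it. Missing-outcome detail is often left to a statistical analysis plan. Here, however, the Protocol has already fixed available-data handling, no replacement and hard count limits together, so the weakness lies in what it fixes.

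**Conclusion.** The point holds in a limited form. For an operated, consenting patient who misses the day-30 visit, a complication not otherwise known to the centre enters the decision as no event, and the error can only favour a finding of safe. The direction follows from the text and needs no assumption about rates.

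The size does need assumptions. With half the risk unseen, alpha moves from 0.0498 to about 0.054, 0.059 or 0.069 for 1, 2 or 4 missed visits in stage 2. This is modest inflation of a rule that has no reserve, and worth correcting because prevention is cheap. It does not undermine the design or the sample size.

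A reader might also infer that every unknown patient should be counted as an event in the binding rule. The calculation argues against that. It is far from slightly conservative, since a single such patient can cost 13 to 15 points of power and, if in stage 1, raise the chance of a false interim stop from 0.062 to 0.152.

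**What to change.** Add to section 11.5:

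- For any missed day-30 visit, the 30-day status for complication, re-operation and death is actively obtained by telephone and from hospital or treating-physician records, before the interim and final counts are made.
- The number of operated patients whose 30-day status remains unknown is reported.
- Beside the available-data decision, a worst-case sensitivity result counts those patients as events.
- At the interim, which is triggered by inclusion of the 22nd participant, patients who have not yet reached day 30 are listed separately from those whose status is unknown.

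The cost is a few telephone calls and one extra line of analysis. The limits and the sample size stay as they are.

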2.7 Patient Information and Informed Consent

The Investigators explain to each subject the nature of the investigation, its purpose, the procedures involved, the expected duration, the potential risks and benefits and any discomfort it may entail. Each subject is informed that the participation in the investigation is voluntary and that he/she may withdraw from the investigation at any time and that withdrawal of consent will not affect his/her subsequent medical assistance and treatment. The subjects are informed that he/she can ask any question, and consult with family members, friends, their treating physicians or other experts before deciding about their participation in the investigation. Enough time is given to the subjects

The subjects are informed that authorised individuals other than their treating physician may examine his/her medical records.

All subjects are given a subject information sheet and a consent form describing the investigation and providing sufficient information for the subjects to make an informed decision about their participation in the investigation. The enrolment will be performed during the outpatient consultation used to plan the bariatric procedure. The bariatric procedure will be done at least five days after this consultation, and patients can until then retract their consent if they do not want to participate in this study. No participant will be included in an emergency situation.

The formal consent of a subject, using the approved consent form, is obtained before the subject is submitted to any investigation procedure.

The subject should read, understand, and voluntarily agree before signing and dating the informed consent form, and is given a copy of the signed document. The consent form is signed and dated by the subject and the Co-Investigators (or her/his designee). The signed consent form is retained as part of the investigation records.

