6. CLINICAL INVESTIGATION DESIGN

6.1 General clinical investigation design and justification of design

Our study will evaluate the feasibility and safety of Senhance™ Surgical System in bariatric surgery at a single center. Therefore we plan to perform a prospective open observational single-center study with the advantage of less bias and confounding factors than in a retrospective study. To achieve a reasonable number of participants and to minimize selection bias we plan to offer robotic operation to all eligible patients. A randomized controlled trial with conventional laparoscopic is not yet feasible as we have to evaluate the feasibility and safety of this procedure first, as we recently introduced it in our centre.

The robot was introduced in June 2021 in our clinic and the first bariatric operation was performed on 28.06.2021. Due to a delay of our application to the CEC because of the new application procedure for medical devices, the approval for our study will come after the first operated patients. Nevertheless, deduced from other teams evaluating robotic operations we believe to still be in the learning curve at the beginning of the study.

No blinding is possible in our study. We plan to include 39 participant in our study which will be operated with our robot. The inclusion period will last 12 months and the follow-up 30 days.

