8.4 Data Collection and Follow-up for withdrawn subjects

Participants can, at any time of the study and, for any reason, withdraw their informed consent in verbal or written form. This withdrawal will lead to participant's exclusion from the study.

If the bariatric operation is already performed, the follow-up will be performed as usually done in our bariatric center (with clinical control at 1, 3, 6, and 12 months during the first year, then each 6 to 12 months during the following years). The clinicopathological data and outcome until withdraw will be collected for safety reasons and will be included in the study.

If the bariatric operation has not yet been performed, but the patient still wants to benefit from a bariatric procedure, bariatric procedure will be performed by laparoscopic technique and the follow-up will be performed in our bariatric center as usual. The clinical data collected before withdrawal will be included in the study.

If the bariatric operation has not yet been performed, and the patient does not wish to benefit from it, he will be redirected to a conservative weight loss program according to the situation. The clinical data collected prior to the withdrawal will be used in the study.

The medical follow-up of withdrawn subjects, or of subjects that drop out from the investigation prematurely is described in chapter 9.2.5 and chapter 9.2.6.

No further data is collected after patients' withdrawal. Health-related personal data will be stored in an anonymized manner after completion of data evaluation.

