10.4.2 Reporting of Safety related events

Reporting to the Sponsor:

All SAEs, device deficiencies and health hazards that require measures are reported to the Sponsor-Investigator by the Co-Investigators (or authorized designee) within 24 hours after becoming aware of the event. Device deficiencies are assessed regarding their potential to lead to an SAE. DD are assessed regarding their potential to lead to an SAE.

Pregnancies

On the day of the operation each female participant that can be pregnant (except hysterectomy, postmenopausal) will have a pregnancy test. If the test is positive, the operation will be reported and the participant excluded from the study.

Reporting of pregnancies after the operation is not necessary.

Reporting to the Competent Ethics Committee:

The Sponsor-Investigator reports to the CEC promptly any serious adverse event which has a causal relation with the MD, comparator or procedure/test method or where a causal relation appears to be possible (Art. 33 ClinO-MD).

In order to ensure prompt notification, the Sponsor-Investigator may initially submit an incomplete notification.

If safety and health hazards that require measures must be taken immediately during the conduct of the investigation, the Sponsor notifies the CEC within 2 days of these measures and the circumstances which made them necessary (Art. 34 ClinO-MD).

Periodic safety reporting (Art. 35 ClinO-MD):

An Annual Safety Report (ASR) is submitted by the Sponsor-Investigator to the CEC, yearly. The ASR contains a list of all SADEs and DDs and a report on their degree of seriousness, causal relationship with the MD and procedure and on subjects' safety.

Other reporting is done according to provisions of MD vigilance as per Art. 87-90 MDR (Art. 33 abs 4.b ClinO-MD) and Art. 67 MedDO.

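### Patients are included before surgery and drop-outs are not replaced, so the fixed limit of fewer than 6 events may be applied to fewer than 39 robot-operated patients

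*Protocol*

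**What the plan says.** Protocol 11.2 fixes the final rule as an absolute count: "Final analysis will be done at 39 patients. Robotic surgery can be regarded as successful if less than 6 events occurred". The interim rule in the same section stops the trial at 5 or more events in 22 patients, and 11.4.4 triggers that look by the number of participants included. No limit is given for any other number of patients.

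On losses, 11.5 states "Drop-outs will not be replaced". Missing values are not imputed.

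On timing, 2.7 places enrolment at the outpatient consultation that plans the operation, and continues: "The bariatric procedure will be done at least five days after this consultation, and patients can until then retract their consent". Section 9.3.1 likewise says that a willing patient who meets the criteria is included at that visit.

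The protocol names two ways of leaving between inclusion and the robotic operation:
- **Withdrawal of consent (8.4).** The patient has a laparoscopic operation or none, and "The clinical data collected before withdrawal will be included in the study".
- **Positive pregnancy test on the day of surgery (10.4.2).** "If the test is positive, the operation will be reported and the participant excluded from the study".

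Two passages point to operated patients as the intended unit. Section 6.1 says "We plan to include 39 participant in our study which will be operated with our robot", and 11.4.1 describes the analysed patients as those having a robotic bariatric operation.

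**The concern.** A patient who is included but never operated with the robot cannot have a complication of robotic surgery. If such a patient is not replaced, the number exposed falls below 39 while the permitted number of events stays at 5. The rule then becomes easier to pass, and the error goes in the unsafe direction: a platform at the unacceptable complication rate is more likely to be called successful. Safety is the primary outcome, and this rule is the only formal decision in the trial.

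**Working it through.** **Inputs**
- Unacceptable rate, 11.2: "we set the maximum acceptable threshold of complications at 25"%, so p = 0.25.
- Expected rate, 11.2: "Literature shows a complication rate for conventional laparoscopic bariatric surgery of 10"%, so p = 0.10.
- Stage 1, 11.2: 22 patients; continue with 4 or fewer events.
- Final, 11.2: 39 patients; success with 5 or fewer events.
- Error rates, 11.2: Type I error 0.05. The stated Type II error of 0.8 is read here as power 0.80.
- Number lost before surgery: not given, so 1 to 5 is assumed.

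**Formula**

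With n operated patients in total, 22 of them in stage 1:

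P(success) = sum over x = 0 to 4 of P[Bin(22, p) = x] × P[Bin(n − 22, p) ≤ 5 − x]

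**The plan's own design, n = 39, p = 0.25**

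| x | P[Bin(22) = x] | P[Bin(17) ≤ 5 − x] | product |
|---|---|---|---|
| 0 | 0.00178 | 0.76531 | 0.00137 |
| 1 | 0.01308 | 0.57389 | 0.00751 |
| 2 | 0.04578 | 0.35302 | 0.01616 |
| 3 | 0.10174 | 0.16370 | 0.01666 |
| 4 | 0.16109 | 0.05011 | 0.00807 |

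The sum is 0.0498. The same formula at p = 0.10 gives 0.802. The stated rule therefore meets a Type I error of 0.05 and power of 0.80, but with a margin of only 0.0002 on the Type I error.

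**One patient fewer, n = 38, p = 0.25**

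Stage 2 now has 16 patients. The products are 0.00145 + 0.00824 + 0.01854 + 0.02005 + 0.01023 = 0.0585.

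**Range of assumed losses, limits unchanged**

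| Operated | Lost | P(success) at 25%, all losses in stage 2 | P(success) at 25%, all losses in stage 1 | P(success) at 10%, all losses in stage 2 |
|---|---|---|---|---|
| 39 | 0 | 0.0498 | 0.0498 | 0.802 |
| 38 | 1 | 0.0585 | 0.0590 | 0.817 |
| 37 | 2 | 0.0686 | 0.0696 | 0.831 |
| 36 | 3 | 0.0800 | 0.0819 | 0.845 |
| 35 | 4 | 0.0930 | 0.0961 | 0.857 |
| 34 | 5 | 0.1077 | 0.1124 | 0.869 |

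The stage 1 column uses 22 minus the losses at the interim look, with the stopping limit still at 5. A single loss takes the error above 0.05, and five losses more than double it. The stage at which losses occur matters little.

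**The case against.** The strongest reply is that a patient who leaves before surgery is a screening failure, not a drop-out. The investigation schedule labels the pre-operative visit as screening and marks the eligibility check at day 0. The inclusion criteria in 7.1 require a bariatric operation with the device. Sections 6.1 and 11.4.1 speak of robot-operated patients. On that reading, the ban in 11.5 covers only losses after the operation, and recruitment would run until 39 are operated.

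This reading is possible and may be what was meant, but the text does not secure it. Sections 2.7 and 9.3.1 call these patients enrolled or included at the consultation, 11.4.4 counts by inclusion, and nothing says that recruitment continues until 39 are operated. The protocol is ambiguous on a number that its error rate depends on.

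Three stronger readings are tempting, and the text does not support them:
- **That 6.1 and 11.5 flatly contradict each other.** Under the screening-failure reading they are compatible.
- **That eligibility is tested only on day 0, which would make late exclusions common.** The schedule marks only that visit, but 7.2 and 9.3.1 also apply the criteria at enrolment.
- **That 8.4 keeps unoperated patients among the 39 as certain non-events.** It keeps only their data up to withdrawal and says nothing about the denominator of the safety rule, while 11.4.1 points the other way.

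It can also be said that the likely loss is small, that this is a pilot to be followed by a randomised study (3.5), and that not replacing drop-outs is an ordinary choice. The first of these stands as a limit on size: one or two losses mean 5.9% to 6.9%. The handling of a different attained sample size is often left to an analysis plan. Here, however, the protocol itself fixes the limit, the 39 and the ban on replacement, and replacement has to be settled while patients are being recruited.

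**Conclusion.** The point holds as an ambiguity with an unsafe direction. Read literally, the protocol allows a success limit derived for 39 exposed patients to be applied to fewer. The chance of calling a platform with a 25% complication rate successful then rises from 4.98% to 5.9% with one loss, and to 10.8% with five.

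The direction does not depend on the number lost, but the size does. The range of 1 to 5 is an assumption, since the protocol gives no rate. The figures also assume independent patients with a common complication rate, and a known 30-day outcome for everyone operated.

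**What to change.** In 11.2, 11.4.4 and 11.5:
1. Define 22 and 39 as patients in whom the robotic operation was started. A patient converted after the start then still counts.
2. State that included patients who never start it are replaced and listed separately, and that recruitment continues until 39 have started.
3. State that the no-replacement rule applies only after the robotic operation has started.
4. If 39 are nevertheless not reached, report the exact attained Type I error for the number operated, from the formula above.

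With 39 operated and their outcomes known, the error returns to 4.98% and the power to 0.802.

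The cost is a few extra consents and slightly longer recruitment, with the number operated unchanged at 39. At assumed pre-operative losses of 5%, 10% and 15%, the number to include is 39/0.95 = 41.1, 39/0.90 = 43.3 and 39/0.85 = 45.9, which round up to 42, 44 and 46.

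Lowering the success limit to 4 or fewer events is not advised as a default. With 38 operated it would bring the error to 2.4%, but the chance of success at a true 10% rate would fall to 0.67.
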